#### **D. Conclusions**

The prevalence of OUDs in the US is alarming and women appear to be at particular risk for overdose death. In spite of this, little is known about gender-specific treatment for opioid dependence. Evidence from a number of sources demonstrate that drug-dependent women show a greater response to stress-inducing stimuli and greater noradrenergic sensitivity as compared to men. Moreover, several studies suggest that alpha-2 agonists, which decrease noradrenergic activity, may be useful in stress-induced craving and relapse in OUDs and studies in cocaine and nicotine dependence suggest that women are more responsive to these agents compared to men. In addition, we have promising preliminary data suggesting that interventions targeting stress vulnerability may be particularly effective in relapse prevention for opioid-dependent women. However, to our knowledge, there are no previous or ongoing studies investigating gender differences in the impact of alpha-2 agonists in decreasing stress-induced craving or relapse in OUDs. We have assembled a multidisciplinary team which includes experienced senior investigators as well as promising and productive junior investigators who will solidify their interest and increase their expertise in sex- and gender-based research through working on this important project. This project will provide important information about a novel treatment strategy which may demonstrate preferential efficacy in the treatment of women with OUD.

## **PROTECTION OF HUMAN SUBJECTS**

### 1. RISKS TO THE SUBJECTS

## a. Human Subjects Involvement and Characteristics 136

Admission into the study is open to men and women and to all racial and ethnic groups, age 18-60. individuals with opioid use disorders (68 men and 68 women) will be recruited primarily through local substance use treatment facilities. Inclusion/exclusion criteria that apply to all participants are listed below:

# General Inclusion / Exclusion Criteria Inclusion Criteria

- 1. Able to provide informed consent and function at an intellectual level sufficient to allow accurate completion of all assessment instruments.
- 2. Meet DSM-5 criteria for opioid use disorder (within the past three months). While individuals may also meet criteria for mild use disorders of other substances, they must identify opioids as their primary substance of abuse and must not meet criteria for any other moderate or severe substance use disorder (except tobacco, caffeine, or marijuana) within the last 60 days.
- 3. On a stable dose of daily buprenorphine or methadone for at least 2 weeks.
- 4. Age 18-65.
- 5. Women of childbearing potential must agree to use an effective means of birth control.
- 6. Consent to remain abstinent from opioids during the 1-week baseline assessment period.
- 7. Must consent to random assignment.

#### **Exclusion Criteria**

- 1. Women who are pregnant, nursing or of childbearing potential and not practicing an effective means of birth control.
- 2. Evidence or history of major medical illnesses, including liver diseases, abnormal vaginal bleeding, suspected or known malignancy, thrombophlebitis, deep vein thrombosis, pulmonary embolus, clotting or bleeding disorders, heart disease, insulin-dependent diabetes, history of stroke or other medical conditions that the investigator deems as contraindicated for the individual to be in the study.
- 3. History of or current psychotic disorder or bipolar I affective disorder.
- 4. Current suicidal or homicidal ideation/risk.
- 5. Taking medications known to act on adrenergic systems (B-blockers; alpha agonists or antagonists)
- 6. Hypotensive individuals with a sitting blood pressure of < 90/50
- 7. QTc interval of >440 in males and > 460 in females as the combination of lofexidine plus methadone may increase the QTc interval. For males with a QTc of greater than >440, but less than 470 AND absence of any history of CV disease AND absence of family history of CV death, they are eligible for enrollment. For females with a QTc of greater than >460, but less than 490 AND absence of any history of CV disease AND absence of family history of CV death, they are eligible for enrollment.
- 8. Known allergy to lofexidine
- 9. Unable to comply with study procedures or pose threat to study staff.

## b. Sources of Materials

Research material obtained from individual participants includes questionnaires and interviews with study personnel, ambulatory assessment data, and blood, saliva and urine samples. To ensure confidentiality, all participant data will be letter/number coded, and only the investigators will have access to the master lists of codes. The research material will be obtained specifically for research purposes. Written research material obtained will be stored in the Addiction Sciences Division or at Shoreline Behavioral Health, in an office that is locked when not in use. Saliva samples will be stored and processed in the Medical University of South Carolina Research Nexus Laboratory. MUSC staff at Shoreline will collect saliva samples, freeze and store them on site, and then send to MUSC for processing.

#### c. Potential Risks

1. Risks due to lofexidine: A Cochrane review provides a comprehensive overview of adverse events associated with lofexidine and other alpha-adrenergic agents (Gowing et al., 2009). Adverse events associated with lofexidine are primarily related to its alpha-adrenergic agonist effects. Hypotension has been reported (Yu et al., 2008; Gowing et al., 2009; Khan et al., 1997), but generally this was mild and studies comparing lofexidine with other alpha-agonists found that hypotension was seen less frequently with lofexidine. Rebound increase in blood pressure after lofexidine discontinuation has also been reported (Yu et al., 2008), but was not severe enough to require intervention. Sedation, dizziness and dry mouth have also been reported with lofexidine at higher rates than placebo, but lower when compared to other alpha-agonists (Khan et al., 1997; Gowing et al., 2009). A case report (Schmitter et al., 2004) and a dose escalation study (Schmitter et al., 2009) report QTc interval prolongation in individuals with lofexidine added to methadone, but there have been no reports of QTc prolongation with lofexidine monotherapy.

- 2. Risks due to study procedures: Participants will be asked not to use illicit opioids for 7 days, however all will be stabilized on buprenorphine or methadone so there should be no risk of opioid withdrawal symptoms.
- 3. Potential risks of rating scales and questionnaires: These are all non-invasive, should add no risk, and have been used without difficulty or any adverse events in our previous studies. The only minor inconvenience could be the time taken to complete them. Some participants may feel uncomfortable disclosing personal thoughts and feelings.
- 4. Risks of stress induction procedures: There is a small risk of increased stress or opioid craving as a result of the CREMA procedures; however, it will likely not differ substantially from the reactivity elicited by stimuli commonly encountered in the day-to-day environment of study participants. Participants that report sustained significant stress or craving after the laboratory session will be provided a debriefing to address symptoms.
- 5. Risks of loss of confidentiality: Careful efforts aimed at maintaining confidentiality have been effective in previous research, and only participants' code numbers will be recorded on the forms themselves to protect confidentiality. Phones provided by study staff to participants will be password protected to limit access to study assessments and pictures; participants utilizing their own phones will be asked to password protect their device for the duration of the study.

## 2. ADEQUACY OF PROTECTION AGAINSTS RISKS

## a. Recruitment and Informed Consent

Potential study participants will primarily be recruited through local treatment settings. Medical records will not be reviewed to identify potential study participants. The study PI, a Co-I, or other qualified study staff will obtain informed consent. The informed consent form includes a detailed description of the study procedures, along with statements regarding participants' rights to withdraw from the procedure at any time without consequences. The informed consent form will be explained to participants in easy-to-understand language, and subjects will be instructed to read the form carefully prior to signing it. Consent will be documented by the signature of the participant on the informed consent agreement, accompanied by the signature of the individual obtaining the consent.

#### b. Protections Against Risks

All study participants will be closely monitored for psychiatric and medical stability. All sessions will be conducted under the supervision of experienced personnel. If crisis intervention is necessary, senior staff will be available to evaluate the subject and provide an intervention or referral. If hospitalization is indicated, the patient will be hospitalized through the Center for Drug and Alcohol Programs at MUSC or an appropriate referral will be made. All participants will be fully informed that they may withdraw from the study at any time without penalty.

Lofexidine will be titrated over ten days when it is initiated. Participants will be seen by a medical provider on three times a week uring dosage escalation and orthostatic hypotension testing will be done. The medical provider will inform the participant, verbally and with a hand-out to take home, concerning common side effects of lofexidine (dizziness, somnolence, dry mouth) and precautions to minimize risks associated with blood pressure decreases (hydration, standing up slowly). The target dose of lofexidine is 2.16 mg per day, but if hypotension or other troublesome side effects develop, the medical provider may slow the titration for that individual. At the end of the study, medications will be tapered over a five-day period. Participants will be seen every other day during medication taper and blood pressure will be monitored.

To ensure confidentiality, all participant data will be coded by letters and/or numbers, and only the investigators will have access to the master lists of codes. All participant records will be kept in a locked cabinet in an office that will be locked at times when not in use. Participants who screen remotely and have virtual medication monitoring visits will be instructed to find a private location to conduc these visits. The research staff understands the importance of maintaining confidentiality, and this method of maintaining confidentiality has been used for several years by our research group and has been effective. All electronic databases are stored on HIPAA-compliant servers with restricted access. All co-investigators and study personnel have completed (or will complete upon hiring) training in Good Clinical Practices as mandated by NIH and the MUSC IRB.

Participants will be taught about potential side effects of lofexidine, and will be closely followed by psychiatrists, a PharmD, and other members of the research team. Pregnancy tests will be performed prior to lofexidine administration. Adverse events will be monitored throughout the study. A member of the research staff will be available to discuss management of any craving urges if craving remains elevated at the end of any study procedures.

## 3. DATA SAFETY AND MONITORING PLAN

This section is based on the recommendations in NIDA's "Guidelines for Developing a Data and Safety Monitoring Plan" (www.drugabuse.gov/funding/dsmbsop.html). A detailed DSMP will be developed and approved by NIH program staff prior to study initiation.

## 1. Summary of the Protocol.

This application proposes to investigate the effects of lofexidine on stress-induced craving and relapse. The primary outcome of interest is stress reactivity. Inclusion/exclusion criteria are outlined above. Power calculations and sample sizes are in the Data Analysis Plan section above.

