|            | 10:15am         | Subjective, physiologic, endocrine measurement             |  |  |
|            |                 |  |  |  |
|            | 815am           | UDS, Saliva  |  |  |
|            | 8:35am          | Relaxation   |  |  |
| Day 2      | 8:55am          | Baseline 1: Subjective, physiologic, endocrine measurement |  |  |
|            | 9:00am          | Opioid imagery/TSST  |  |  |
| Test       | 9:05am          | Subjective, physiologic, endocrine measurement             |  |  |
| _          | 9:10am          | Subjective, physiologic, endocrine measurement             |  |  |
|            | 9:35am          | Subjective, physiologic, endocrine measurement             |  |  |
|            | 10:05 am        | Subjective, physiologic, endocrine measurement             |  |  |

will provide a urine sample to be tested for drugs of abuse. For women, a pregnancy test will be done prior to the urine drug screen, and saliva will be collected for estrogen and progesterone measurement.

- **b.Progesterone and Estrogen.** As there is significant individual variability in progesterone and estrogen levels across the menstrual cycle, measurement of progesterone and estrogen at the time of testing in combination with the menstrual cycle history will allow us to approximate the menstrual cycle phase as well as to utilize all participants' data with absolute progesterone and estrogen levels as continuous measures.
- **c. Design timing.** Subjects will first undergo a progressive relaxation task. Baseline assessments of subjective, hormonal (cortisol), and physiologic measures (blood pressure and heart rate) will be collected following relaxation, 5 minutes before the stressor or imagery; TSST takes 15 minutes, and the imagery takes 5 minutes. At the end of the stressor of drug cue, a salivary sample will be collected to assay cortisol and physiological (blood pressure and heart rate) and subjective measures (Mood Rating Scale, Opioid Craving Questionnaire, STAI) will be obtained. Measurements will also be obtained at 5- 30-, and 60-minutes post-task.
- d. Trier Social Stress Task (TSST) is a standardized psychological stress challenge which has been used extensively in research studies. A meta-analysis supports its utility for evoking a HPA axis stress response in a laboratory setting (Dickerson & Kemeny, 2004). It has induced a robust and reliable physiological stress

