Statistics and Data Analysis (complete statistical/data analysis plan in Biostatistics Resource Core): Aim 1: Using a human laboratory paradigm, determine the impact of lofexidine on stress and drug cueinduced craving in women and men with OUDs: The primary study outcome of interest in Aim 1 is the differential craving, stress and anxiety response to a human laboratory paradigms containing both a stressor (TSST) and an opioid specific cue between participants randomized to lofexidine and placebo in addition to buprenorphine/methadone maintenance. Hypothesis 1: Lofexidine will attenuate drug craving and subjective stress response to a stress task in opioid-dependent individuals compared to individuals receiving placebo. Hypothesis 2: Lofexidine will attenuate drug craving and subjective stress response to a drug-related cue in opioid-dependent individuals. Hypothesis 3: The ameliorative effects of lofexidine on stress and cue-reactivity will be more pronounced in females than male subjects. To assess the hypothesis that lofexidine will attenuate drug craving and subjective stress response to the stressor and the opioid-related cue task, multilevel longitudinal GLMMs will be developed using all post-stressor and post-cue data. Initial models will control for study design aspects such as order (stressor or cue first), treatment assignment, and baseline craving and stress (task level). Covariate adjusted models will additionally include baseline characteristics determined to be correlated with study outcomes or those determined to be significant effect modifiers. To examine the differential effects of lofexidine on stress and cue-reactivity across female and male subjects, the models will have additional parameters added to include an indicator of participant gender and the interaction between gender and randomized treatment assignment. Relevant interactions will be assessed in all models. Least square means and associated standard errors will be assessed to compare craving and subjective stress response between treatment assignments at all time points.

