Aim 2: To evaluate the impact of lofexidine on opioid craving and subjective experience of daily stressors in men and women with OUDs: The primary measures of interest for Aim 2 are craving and stress ratings in response to stress-related cues using *Cue Reactivity Ecological Momentary Assessment* (CREMA) as well as subjective experiences of daily life stressors Hypothesis 1: Lofexidine will decrease craving and decrease the subjective experience of daily stressors in opioid-dependent men and women. Exploratory Hypothesis 2: Lofexidine will be more efficacious in decreasing stress-related craving in opioid-dependent women as compared to men. To assess this hypothesis a multilevel generalized linear mixed effects models with repeated measures (GLMMs) will be developed using CREMA session response data from the 5-week period during study medication administration. Pre-cue stress and craving rating will be centered and used as a time varying covariate in all analysis. Additionally, CREMA cue response data during the 7 day baseline assessment period will be used as a time naïve covariate in all analyses. Least squares means and associated standard errors will be used for post-hoc comparisons of craving and stress response between women and men over time. Models developed to address hypothesis 2 will be utilized to examine the impact of gender on opioid use and stress-related craving during study treatment. All other relevant interactions will be assessed in all models.

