## Power and Sample Size (complete sample size justification available in Biostatistics Resource Core):

The current study is powered on the primary Aims 1 and 2. In the proposed study, response to a laboratory stressor, CREMA cue response and daily use data will be tested using GLMMs (assuming a Gaussian distribution) and the study will be powered to sufficiently address the least of the study treatment effect sizes determined to be clinically meaningful for the study hypothesis. Aim 1: Sinha and colleagues (Sinha, et al 2007), in a small pilot sample, demonstrated that lofexiding in combination with naltrexone attenuated craving and anger in response to laboratory drug and stress cues as compared to naltrexone alone. Results indicate a larger change in opioid craving scores in response to drug-related and stress cues occurs in placebo participants than lofexidine treated participants [Drug related cue response  $\Delta$ =2.2; SDP=2.6; between group Cohen's d=0.85, p<0.05 and stress cues response  $\Delta$ =2.1; SDP=2.4; between group Cohen's d=0.88, p<0.05]. Moreover, Fox and colleagues (2014) conducted a trial of quanfacine in cocaine-dependent individuals and noted stress and craving response to stress and drug-related imagery. They noted significant gender differences across treatment assignment for craving and stress response to drug-related imagery [Craving  $\Delta$ =3.0; SDP=3.8; Treatment x Sex Intx Cohen's d=0.79, p<0.05; Negative Emotion  $\Delta=3.0$ ; SDP=2.9; Treatment x Sex Intx Cohen's d=1.0, p<0.05]. Sample sizes in both the Sinha and Fox studies were somewhat small. Smaller but still clinically relevant effect sizes in an adequately powered study are anticipated. Therefore, a 20% reduction in craving and stress response from the previous studies is anticipated in the current design (Cohen's d=0.64 for the sex x treatment interaction on craving response). Aim 2: Kowalczyk and colleagues (2015), showed that daily life craving reports as measured by EMA were significantly reduced in opioid using participants randomized to clonidine as compared to placebo [6.3% (95% CI=5.6-7.1) vs. 11.8% (10.9-13.0); between group Cohen's *d*=1.6]. To assess the least of the differences anticipated in project 2, a sample size of 39 participants randomized to each female and males across active lofexidine and placebo groups would provide 80% power with a type 1 error rate of 5% to detect the treatment x sex interaction in craving and stress response to laboratory drug based cues (total n=156; 78 per group). We anticipate 25% attrition between randomization and the end of the 5-week active treatment period. Thus, inflating the necessary sample size to 68 participants randomized per treatment group with a total of n=136 randomized participants will provide adequate power.

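### The protocol names no single primary outcome or test, and no visible rule divides its one 5% error rate among the 8 to 12 tests in Aim 1

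*Combined protocol and SAP*

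**What the plan says.** Four places bear on which outcome is primary.

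- **Data Safety and Monitoring Plan, item 1 (Summary of the Protocol):** "The primary outcome of interest is stress reactivity". It gives no instrument, task or time point.
- **C.2.d, Aim 1:** "The primary study outcome of interest in Aim 1 is the differential craving, stress and anxiety response to a human laboratory paradigms", where the paradigm comprises both the stress task (TSST) and an opioid cue. Hypotheses 1 and 2 cover craving and subjective stress after each task, and hypothesis 3 adds a larger effect in women. Least squares means will also be used to "compare craving and subjective stress response between treatment assignments at all time points".
- **C.2.d, Aim 2:** "The primary measures of interest for Aim 2 are craving and stress ratings in response to stress-related cues", together with the experience of daily stressors. Hypothesis 2 of this aim is labelled exploratory, as is the whole of Aim 3.
- **Power and Sample Size:** Aims 1 and 2 are both called primary. The effect size is "Cohen's d=0.64 for the sex x treatment interaction on craving response", and the sample size is chosen "to detect the treatment x sex interaction in craving and stress response to laboratory drug based cues", with 80% power and a 5% type 1 error rate.

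The measures are not fixed to one instrument either. The laboratory subjective measures are listed in C.2.c.5 Phase Two (Design timing) as "Mood Rating Scale, Opioid Craving Questionnaire, STAI". The CREMA section says the mood scale itself contains a craving item, and the Assessments paragraph says that scale is reused in the laboratory and that craving is also rated in a Likert format.

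C.2.d and the sample size section both say that the complete versions of the analysis plan and sample size justification are held in the Biostatistics Resource Core.

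**The concern.** A reader of these documents cannot tell which result will decide whether the trial met its primary aim. The safety-plan summary omits craving and the drug cue, yet the effect size was taken from craving and the sample size sentence concerns the drug cue. Several outcomes, two tasks and two effects (treatment, and treatment by gender) all sit under a primary aim. Only one 5% error rate is stated, and it belongs to one test. If each of these tests is read at 5%, the error rate for the set is well above 5%. The choice of scale and time point adds further ways to obtain a nominally significant result.

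**Working it through.** **1. Reproduce the stated sample size.** Inputs from Power and Sample Size: d = 0.64, 80% power, 5% error rate. Sidedness is not stated. For two groups, n per group = 2 × ((z for alpha + z for power) / d)².

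- Two-sided 5%: 2 × ((1.960 + 0.842) / 0.64)² = 38.3, so 39. Four cells give 4 × 39 = 156, which matches the plan.
- One-sided 5% gives 31, which does not match.

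The stated 39 therefore uses the whole two-sided 5% for one comparison. No alpha was kept back for a second test.

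**2. Count the Aim 1 tests.** This count is derived from the text; the plan does not state it.

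- Outcomes named in hypotheses 1 and 2 (craving, subjective stress): 2 outcomes × 2 tasks × 2 effects = 8.
- Adding anxiety, which appears in the primary-outcome sentence but not in those hypotheses: 3 × 2 × 2 = 12.

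**3. Chance of at least one false positive at 5% each.** For k independent tests this is 1 − 0.95^k. For correlated tests it was simulated with multivariate normal statistics. The correlations are assumptions, and the treatment and interaction effects were taken as independent of each other (balanced design).

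| Correlation between outcomes / between tasks | 8 tests | 12 tests |
|---|---|---|
| 0 / 0 (formula) | 33.7% | 46.0% |
| 0.3 / 0.3 | 32.2% | 43.4% |
| 0.5 / 0.5 | 29.8% | 39.0% |
| 0.7 / 0.5 | 27.6% | 34.7% |
| 0.8 / 0.7 | 23.9% | 29.4% |

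Aim 2, the contrasts at the four post-task times (end of task, then 5, 30 and 60 minutes) and the covariate-adjusted models are not counted.

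**4. Cost of spreading alpha equally instead of naming one test.** Bonferroni, d = 0.64, same two-group formula:

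- 8 tests: 0.05 / 8 = 0.00625 each; 63 per group needed; power at 39 per group falls from 0.81 to 0.54.
- 12 tests: 0.05 / 12 = 0.00417 each; 68 per group needed; power at 39 falls to 0.48.

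With one pre-named test at 5%, the alpha used in the stated calculation stands.

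**5. What the randomized number leaves for that one test.** 136 × 0.75 = 102 completers, and 102 / 4 = 25.5 per cell. Keeping 156 after 25% attrition would need 156 / 0.75 = 208 randomized. Putting 25.5 in place of 39 in the plan's own two-group calculation gives power of about 63%. If d = 0.64 is a difference of differences in SD units, its variance is 4/n, and power is about 51% at 39 per cell and about 36% at 25.5.

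**The case against.** The safety-plan sentence sits in a short summary that refers back to the analysis section for power. Its neighbouring sentence speaks of craving and relapse induced by stress, so the phrase may be shorthand. That is plausible, but the sentence as it stands still leaves out craving and the drug cue and needs aligning.

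A reader might infer that the primary outcome is declared in three incompatible ways, and that the trial was sized on something other than the outcome in the summary. The text does not support this. The sample size section is a basis for power, not an outcome declaration, and its operative sentence covers stress response as well as craving. The mismatch is narrower: that sentence concerns drug cues, and its effect size comes from craving.

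The plan is not without structure. A.6 and A.7 make gender differences the primary objective, and Aim 2 hypothesis 2 and Aim 3 are labelled exploratory. This narrows the field but still leaves Aim 1 and the rest of Aim 2 as primary, with no order among them.

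The test count can be disputed. If both tasks were pooled in one model per outcome, 2 outcomes × 2 effects = 4 tests, or 18.5% if independent. Hypotheses 1 and 2 are stated separately by task, however, so 8 is the natural count, and even 4 exceeds 5%. Independence is unlikely for ratings from the same person, so 46% is the top of the range and not the expected value.

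Finally, the plan in the Biostatistics Resource Core may contain a multiplicity rule. The absence noted here is an absence from these documents only.

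**Conclusion.** The point holds for the text available. Four places need reconciling on the primary outcome, and no testing order or adjustment is given. For Aim 1 alone, the chance of at least one false positive is 34% to 46% under independence and roughly 24% to 43% under the assumed positive correlations. This rests on 8 to 12 tests, each read at two-sided 5%. That reading is inferred from the single stated 5% and the lack of any adjustment.

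A reader might go further and conclude that the plan lets the trial claim success on whichever outcome turns out positive. The documents contain no success rule at all, so they neither grant nor rule out such a claim. Each individual test also keeps its own 5%; the inflation concerns the set.

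**What to change.** Before unblinding, name one primary test and use it consistently in C.2.d (Aims 1 and 2), Power and Sample Size, and the safety-plan summary. The choice closest to the stated objective and sizing is the treatment-by-gender interaction on opioid craving response to the drug-cue task, on one named scale, averaged over the post-task times, at two-sided 5%. Make the other Aim 1 tests and all Aim 2 tests secondary under a stated testing order or adjustment. Holm is one option among several. If the Core plan already has a rule, bring it into the protocol instead. Label the contrasts at individual time points descriptive.

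The cost is protocol and analysis-plan wording, and secondary outcomes will need smaller p-values to be claimed. The change does not repair the separate shortfall between 156 required and 136 randomized with 25% attrition. Power for the named test must therefore be restated at the number expected to complete, and the statement should say whether d = 0.64 is a two-group difference or a difference of differences.
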